4.2.1 Definition of a Serious Adverse Event (SAE)

An SAE is any untoward medical occurrence at any dose (including after the Informed Consent Form (ICF) is signed and prior to dosing) that:

- Results in death
- Is life-threatening (patient is at immediate risk of death from the event as it occurred)
- Requires inpatient hospitalization (formal admission to a hospital for medical reasons) or prolongation of existing hospitalization
- Results in persistent or significant disability/incapacity
- Results in a congenital anomaly/birth defect

Important medical events that may not result in death, are not immediately life-threatening, or do not require hospitalization may be considered SAEs when, based on appropriate medical judgment, they may jeopardize the patient and may require medical or surgical intervention to prevent one of the outcomes listed in this definition. Examples of such events include allergic bronchospasm requiring intensive treatment in an emergency room or at home, blood dyscrasias or convulsions that do not result in inpatient hospitalization, or the development of drug dependency or drug abuse.

4.3 Handling of Missing Data

4.3.1 Handling of Missing Dates/Months/Years for Determination of TEAEs

Adverse events with incomplete onset dates will be handled as follows for the purpose of determining treatment emergence according to the definition above.

- If the start/end date of an AE is partially missing, the date will be compared as accurately as possible with the first dose of study drug and the date of last dose of study drug plus 30 days. The AE will be assumed to be treatment-emergent if it cannot be definitively shown that the AE did not start or worsen during the treatment-emergent period.
- If the start date is completely missing, an AE will be considered treatment-emergent unless the stop date is before first dose of study drug.

The original partial or missing date will be displayed in listings of AEs.

4.3.2 Handling of Missing Dates/Months/Years for Concomitant Medications

Prior or concomitant medications with incomplete start dates will be handled as follows for the purpose of determining whether a non-study medication is a concomitant medication:

- If the start/stop date of a medication is partially missing, the date will be compared as accurately as possible with the first dose date of study drug and the last dose date of study drug plus 30 days. The medication will be assumed to be concomitant if it cannot be definitively shown that the stop date is before first dose date of study drug, or the start date is more than 30 days after the last dose date of study drug.
- If the start/stop dates are completely missing, a medication will be considered concomitant.

4.3.3 Handling of Missing Dates for Disease History

For the purpose of calculating the duration from initial diagnosis, partial/missing dates for diagnosis will be imputed as follows:

- If both day and month are missing and the year is prior to the year of screening, the imputed date will be 01 July
- If both day and month are missing and year is the same as the year of screening, the imputed date will be the middle point between 01 January of the year and the screening date. If the middle point falls between two dates, the first of the two dates will be used.
- If day is missing and the month and year are prior to the month and year of screening, the imputed date will be the 15th day of the month.
- If day is missing and the month and year are the same as the month and year of screening, the imputed date will be the middle point between the first day of the month and the screening date. If the middle point falls between two dates, the first of the two dates will be used.
- No imputation will be performed if the year is missing.

4.4 Multiple Comparisons/Multiplicity Adjustment

No adjustment for multiple comparisons will be performed for this study.

4.5 Subgroups

4.5.1 Subgroups based on baseline demographics and disease characteristics

The following subgroups may be examined for key efficacy and safety endpoints.

- Age group (< 65 years vs. \geq 65 years)
- Gender (Male, Female)
- Race (Asian, Black or African America, White, Other)
- Ethnicity (Hispanic or Latino, Not Hispanic or Latino)
- Geographic Region (US, Europe, Japan)
- Baseline BMI (kg/m²; < median, \geq median)
- Baseline ECOG performance status (0, 1, 2)
- Time since initial diagnosis (< median, \ge median)
- Histopathological diagnosis*
- Time since most recent relapse/refractory diagnosis (months; < median, ≥median)
- Initial stage (I/II, III, IV)
- Baseline stage (I/II, III, IV)
- Initial Ann Arbor stage (A, B, E, S)
- Baseline Ann Arbor stage (A, B, E, S)
- Number of prior regimens (1, 2, 3 or more)
- Time since most recent treatment (weeks; < median, \ge median)
- Best response to most recent prior treatment (CR, PR, SD, PD)
- Prior radiotherapy (Yes, No)
- Prior Surgery (Yes, No)
- Prior CHOP (Yes, No)
- Prior CHOEP (Yes, No)
- Prior CHOP or CHOEP (Yes, No)
- Prior Salvage Chemotherapy after CHOP or CHOEP (Yes, No)

- Prior BV-CHP (Yes, No)
- Prior stem cell therapy (Yes, No)
- By major histology (PTCL-NOS, AITL, ALCL, Other)
- Non-AITL vs. AITL
- Non-ALCL vs. ALCL

*Categories for histopathological diagnosis will be based on the data observed and will include distinct categories for each common type (major histologic subtypes), and an "Other" category to combine types with less than 3 patients (minor histologic subtypes).

Prior CHOP will be defined as patients who received cyclophosphamide, doxorubicin, vincristine, and prednisone in a single prior regimen that does not include etoposide. Prior CHOEP will be defined as patients who received cyclophosphamide, doxorubicin, vincristine, etoposide, and prednisone in a single prior regimen. Prior salvage chemotherapy after CHOP or CHOEP will be defined as patients who had any other chemotherapy regimen following a regimen of CHOP or CHOEP. Prior BV-CHP is defined as patients who received brentuximab vedotin, cyclophosphamide, doxorubicin, and prednisone in a single regimen.

4.5.2 **Prognostic factors**

A subgroup analysis for the following prognostic factors and each of their components (where applicable) will be performed for key efficacy endpoints.

- All major histologic subtypes except for anaplastic large-cell lymphoma (ALCL)
- All major histologic subtypes except for Angioimmunoblastic T-cell lymphoma (AITL)
- Baseline international prognostic index (IPI) score and each component
- Received a stem cell transplant post baseline (yes, no)

IPI score is derived by assigning one point for each of the 5 components. A score of 0-1 is considered 'Low', a score of 2-3 is considered 'Intermediate', and a score of 4-5 is considered 'High'. Components:

- Age > 60 years
- Baseline stage III or IV disease
- Baseline ECOG score ≥ 2
- Baseline lactate dehydrogenase > ULN
- 2 or more extranodal lesions (target or non-target)

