2.6.2 Expansion Phase

• Analysis of duration of complete response

- Subgroup analysis of select efficacy and safety endpoints.
- Analysis of PTCL tumor pharmacodynamic markers in relation to PK, safety, and efficacy
- Analysis of PTCL tumor prognostic markers in relation to safety and efficacy
- Analysis of cytokines and non-tumor immune populations in relation to safety and efficacy
- Additional exploratory analyses identified by the Sponsor may be performed on study samples

3 Study design

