4.7 Baseline Values

Unless otherwise specified, the baseline value is defined as the most recent value prior to first study drug administration.

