5.2.1 Analyses of Primary Endpoint

5.2.1.1 Primary Analysis of ORR/BOR

ORR and BOR as determined by both the IRC and the Investigator will be presented along with 2-sided confidence intervals using normal approximation.

Swimmer's plots will be produced with time on study as the x-axis and patient ID along the y-axis. Different symbols representing the study day of each IRC response (CR, PR, SD, PD, NED), end of treatment reason (PD, AE, death, transplant, other), and end of study reason (death, other) will be plotted for each patient. Patients will be grouped by best overall response.

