5.2.1.3 ORR/BOR by prognostic factors

The primary analysis will be repeated by the prognostic factors described in section 4.5.2. A forest plot will be presented for the expansion phase and for all patients combined plotting ORR with 95% CI for each prognostic factor and component.

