5.2.2.3 Analysis of PFS

For the PFS analyses, censoring of PFS will be performed as detailed in Table 2. Note that progression may be documented based on scheduled or unscheduled disease status assessment, and that unscheduled disease status assessments will be included in calculating the gap between adequate disease status assessments.

PFS will be estimated for each cohort using the Kaplan-Meier method. PFS will be plotted by using the Kaplan-Meier method. Number of patients with events, type of events (progression or death), number of patients censored, number of patients for each reason of censoring, Kaplan-Meier estimates and 95% confidence intervals for the 25th percentile, median, and 75th percentile for PFS will be presented. A 2-sided 95% confidence interval for median PFS will be provided by using the Brookmeyer-Crowley method. Probabilities of remaining alive and progression free at selected time points may also be presented.

PFS analysis will be repeated for the subset of enrolled Japanese patients and for each of the prognostic factors described in section 4.5.2

Situation	Date of Event or Censoring	Outcome
No adequate baseline disease status assessment	Date of randomization + 1 day	Censored
No adequate post-baseline disease status assessment unless death occurs prior to first scheduled post-baseline assessment	Date of randomization + 1 day	Censored

Table 2: Primary PFS Censoring/Event Rule

No documented progression or death	Date of last adequate disease status assessment	Censored
Documented progression with ≤1 missing scheduled disease status assessment before progression	Date of the earliest assessment that results in a finding of unequivocal progression	Event
Death before progression being documented with ≤1 missing scheduled disease status assessment before death	Date of death	Event
Documented progression or death following a gap between adequate disease status assessments equivalent to 2 missed visits	Date of last adequate disease status assessment before the gap	Censored
New anticancer treatment or procedure started before documented progression or death.	Date of last adequate disease status assessment prior to start of new anticancer therapy	Censored

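### SAP 4.5.2 treats post-baseline stem cell transplant as a prognostic factor: PFS split by it is biased whenever a transplant precedes progression, and the ORR split may be reverse selection

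*SAP*

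**What the plan says.** SAP 4.5.2 (Prognostic factors) opens with "A subgroup analysis for the following prognostic factors and each of their components (where applicable) will be performed for key efficacy endpoints". The list holds histology exclusions, the baseline IPI score with its components, and "Received a stem cell transplant post baseline (yes, no". Transplant before study entry is a separate item in SAP 4.5.1, so this entry is not a mislabelled baseline variable. The 4.5.1 subgroups are optional; those in 4.5.2 are mandatory.

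Two sections act on the list:

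- SAP 5.2.1.3, for ORR and best overall response: "The primary analysis will be repeated by the prognostic factors described in section 4.5.2". A forest plot follows for the Expansion Phase and for all patients combined.
- SAP 5.2.2.3: "PFS analysis will be repeated for the subset of enrolled Japanese patients and for each of the prognostic factors described in section 4.5.2".

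Three further provisions bear on the point:

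- PFS runs from first dose (SAP 2.5.2).
- SAP Table 2 censors PFS at the last adequate assessment before the event described as "New anticancer treatment or procedure started before documented progression or death".
- The swimmer's plots in SAP 5.2.1.1 carry symbols for "end of treatment reason (PD, AE, death, transplant, other", so transplant is a foreseen reason for ending treatment, listed apart from progression.

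Neither 4.5.2, 5.2.1.3, 5.2.2.3 nor the optional models in 5.2.3 provides a landmark, a time-dependent covariate or a caveat for transplant.

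**The concern.** A prognostic factor has to be known at the start of the clock. SAP 4.7 sets that point: "the baseline value is defined as the most recent value prior to first study drug administration". Transplant after baseline is fixed later, and splitting patients by it uses their future to form the groups.

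For PFS, two mechanisms act in the same direction. A patient transplanted before progression must have survived progression-free to the transplant, which is immortal time credited to the transplanted group. Table 2 does not name transplant, but its wording on a new anticancer treatment or procedure reasonably covers it. If so, that patient is then censored. The transplanted group can show a PFS event only in patients transplanted after progression.

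For ORR, response may be one of the reasons a patient reaches transplant. A higher ORR among transplanted patients would then reflect selection by response and not a baseline characteristic that predicts it.

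The curves and the forest-plot row would appear as pre-specified outputs labelled prognostic, in a study whose results are meant for health authorities and publication (SAP 3.5). More patients would not remove the bias.

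**Working it through.** **The plan's own figures.** The SAP gives none for this contrast. The nearest is 99.2% power for ORR 20% against 40% with 100 patients (SAP 3.3). An exact binomial test rejecting at 29 or more responses (upper-tail error 0.0200) gives 99.16%. That figure reproduces and is not in dispute.

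**Inputs.** The clock start and the censoring rule come from SAP 2.5.2 and Table 2. The 40% ORR is the plan's alternative. Transplant rates, timing and median PFS are assumed, because the documents give none.

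**PFS when transplant does nothing.** All patients have exponential PFS with median 3.5 months. Transplant before progression arises at a constant rate, independent of prognosis. In total 10% are transplanted: a share *f* of them before progression, the rest drawn at random from progressed patients. Patients transplanted before progression are censored at transplant (Table 2 uses the last scan before it).

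- Let *p* = 0.10 × *f* be the proportion of all patients transplanted before progression. The time to whichever comes first, progression or transplant, is exponential with median 3.5 × (1 − *p*).
- Everyone not transplanted progresses, so that group's median is 3.5 × (1 − *p*).
- In the transplanted group only the fraction 1 − *f* have events, so the Kaplan-Meier median is 3.5 × (1 − *p*) / (1 − *f*).

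| *f* | Transplanted: median (months) | Not transplanted: median (months) |
|---|---|---|
| 100% | not reached (no events) | 3.5 × 0.90 = 3.15 |
| 75% | 3.5 × 0.925 / 0.25 = 12.95 | 3.24 |
| 50% | 3.5 × 0.95 / 0.50 = 6.65 | 3.33 |
| 25% | 3.5 × 0.975 / 0.75 = 4.55 | 3.41 |
| 0% | 3.5 | 3.5 |

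Simulation with 1,000,000 patients per case agrees. Six-month PFS was 100% against 26.7% at *f* = 100%, and 53.3% against 28.6% at *f* = 50%.

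**If Table 2 is read as not covering transplant.** Under the same assumptions, without censoring, the medians are 8.0 against 3.15 months at *f* = 100% and 5.6 against 3.3 at *f* = 50%. The immortal time alone separates the curves.

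**A second set of assumptions.** PFS is exponential with median 3, 4 or 6 months. Transplant occurs at months 3–6 if the patient is still progression-free. It is planned in 30% of responders and 0–5% of non-responders, or in 10% of both. A further 0% or 3% of the other patients are transplanted after progression. Follow-up is 18 months and the true ratio is 1.0. The ratio of PFS event rates, transplanted to not transplanted, was:

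- 0 to 0.44 with censoring at transplant;
- 0.45 to 0.68 without it;
- 0.99 to 1.01 with transplant as a time-dependent exposure and no censoring at transplant.

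**ORR.** Let *a* and *b* be the transplant rates in responders and non-responders. With 40% responding overall, ORR is 0.4*a* / (0.4*a* + 0.6*b*) in transplanted patients and 0.4(1 − *a*) / (1 − 0.4*a* − 0.6*b*) in the others.

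| *a* / *b* | Transplanted | Not transplanted |
|---|---|---|
| 10% / 10% | 0.04 / 0.10 = 40.0% | 0.36 / 0.90 = 40.0% |
| 15% / 10% | 0.06 / 0.12 = 50.0% | 0.34 / 0.88 = 38.6% |
| 20% / 5% | 0.08 / 0.11 = 72.7% | 0.32 / 0.89 = 36.0% |
| 25% / 2% | 0.10 / 0.112 = 89.3% | 0.30 / 0.888 = 33.8% |

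Selection need not be deliberate. Suppose responders simply stay progression-free longer: 2 months plus an exponential time with median 6, against an exponential median of 2 in non-responders. Offer transplant equally to both (25% at months 2.5–6 if progression-free, 5% after progression). Simulation then gives ORR 62.1% against 36.5% and median PFS 8.9 against 3.1 months.

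**The case against.** The strongest reply is that the bias is conditional. If every transplant follows progression, the PFS medians agree at 3.5 months; if transplant is equally common in responders and non-responders, ORR agrees at 40.0%. No document says that responders are selected. The end-of-treatment list in SAP 5.2.1.1 gives plot symbols, not progression status, and Expansion Phase patients may stay on drug after progression, so a transplant that ends treatment can still follow it. SAP 4.7 defines a baseline value but does not require every 4.5.2 factor to be one. The groups would be small: 10% of 100–130 patients is 10–13. At 15%/10% with 100 patients the transplanted row has 12 patients and 50% ORR, with a normal-approximation 95% interval of about 22–78%, which covers 38.6%. No test between rows is planned, and the outputs fall under "Subgroup analysis of select efficacy and safety endpoints" among the exploratory endpoints in SAP 2.6.2.

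Much of this stands. The magnitudes are illustrative, the ORR point is a possibility, and the stakes are limited. It does not rescue the PFS split. A transplant reason listed apart from progression reasonably supports some transplants before progression, even though it does not give their share. The immortal time also remains whether or not Table 2 covers transplant. Wide intervals and exploratory status do not make a biased contrast readable as prognostic.

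**Conclusion.** The concern holds. The PFS comparison by post-baseline transplant favours the transplanted group whenever some transplants precede progression, even if transplant has no effect and is unrelated to prognosis. Its direction needs only that condition. Its size depends on the assumed mix and runs, in the first PFS table, from no difference to no events at all in the transplanted group. The ORR row may be reverse selection, to a degree set by transplant practice that the documents do not describe. The primary ORR analysis, its power and the overall PFS are untouched. This should be corrected, but it does not threaten the trial's main conclusion.

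**What to change.** - Delete the transplant item from SAP 4.5.2, and with it the ORR and best-overall-response repeat, the forest-plot rows and the PFS repeat. If the optional SAP 5.2.3 models are fitted, do not enter it as a fixed covariate.
- Add a descriptive table of transplant for all patients, including those transplanted after treatment ended for another reason: number, timing, and response status at transplant.
- If an association with PFS or OS is wanted, specify a time-dependent covariate or a landmark analysis. Add a PFS sensitivity analysis that does not censor at transplant where later scans exist. These may be few, because off-treatment response assessments stop at alternate anti-cancer therapy (Protocol Table 4, note 4).

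The cost is a change of SAP wording and the programming of one table. Relabelling the existing split as descriptive would be lighter, but it would leave the biased PFS curves in place. No interpretable result is lost by deletion.

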4.6 Visit Windows

Treatment visits, cycles, and days are pre-defined for this study and are pre-specified on the CRF. In the presentation of study data using Study Day and Cycle Day, the following derivations will be used:

- Day 1 of Study = Date of first dose for a patient
- Study Day = Date Date of first dose + 1, if Date is on or after Date of first dose or Study Day = Date Date of first dose, if Date is before Date of first dose

- Day 1 of Cycle = Date of cycle start, as reported on eCRF (per protocol, Day 1 of Cycle 1 should be Day 1 of Study)
- Cycle Day = Date Date of cycle start in current cycle + 1

4.7 Baseline Values

Unless otherwise specified, the baseline value is defined as the most recent value prior to first study drug administration.

4.8 Computing and Coding Standards

Computing, coding, and grading standards are provided in the following table.

Table 1: Computing, coding and grading standards		
Table, listing, and figure production	SAS Version 9.2 or higher	
Coding		
Adverse Events	Medical Dictionary for Regulatory Activities	
	(MedDRA) Version 20.1 or higher	
Medical Histories	MedDRA Version 20.1 or higher	
Prior and Concomitant Medications	WHODrug Version Mar. 2013 or higher	
Prior and post Systemic Therapy	WHODrug Version Mar. 2013 or higher	
Grading		
AEs	Common Terminology Criteria for Adverse	
	Events (CTCAE) Version 5.0	
Laboratory Results	CTCAE Version 5.0	

5 Statistical Analyses

5.1 Study Subjects

5.1.1 Disposition of Subjects

The number and percentage of patients in each analysis set will be provided. This includes the Safety Analysis Set, mITT and the Dose Optimization Efficacy Set. The percentage will be based on the number of patients in the Safety Analysis Set. Disposition of patients will be summarized for the Safety Analysis Set. The number and percentage of enrolled patients, treated patients, patients entered follow-up, patients who completed the study, and patients who discontinued the study and reasons for discontinuation will be summarized. Disposition of patients will be summarized for the overall population as well as by different cohorts and by phase.

Time to treatment discontinuation will be summarized for subjects who have discontinued treatment at time of data cut-off. Follow-up time (from 1st dose to last contact on or prior to data cut-off) will be descriptively summarized. For responders, follow-up time from first response to last contact on or prior to data cut-off will also be summarized.

5.1.2 **Protocol Deviations**

Protocol deviations will be categorized as major or minor prior to data release for the futility analysis and final analysis of the primary endpoint. A summary table of the major protocol deviations will be provided by cohort and by phases for the mITT Analysis Set. A listing of major protocol deviations will be provided.

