# 4.3. Duration of Patient Participation

The duration of patient participation is dependent on the patient's tolerance of and response to duvelisib; it is anticipated that patients will participate in the study for a minimum of  $\sim$ 3 months.

All patients will be screened for study eligibility within 30 days before the first study drug dose (i.e., Baseline, C1D1). Patients who are determined to be eligible will be enrolled in the study at Baseline and will receive duvelisib continuously in 28-day cycles. For the Dose Optimization Phase, it is anticipated that patients will receive at least 1 cycle of therapy. For the Expansion Phase, it is anticipated that patients will receive at least 2 cycles of therapy. Unlike the Dose Optimization Phase if the patient demonstrates progression and no dose modification was required for toxicity, the patient may re-escalate to 75 mg BID with a confirmatory scan after approximately 4 weeks of therapy. Patients will continue duvelisib until development of PD or intolerance or another discontinuation criterion is met, as determined by the Investigator; no maximum duration of therapy has been set. After discontinuation of duvelisib, all patients are to attend an End-of-Treatment (EOT) visit within 7 days after the last study drug dose and then a Safety Follow-up visit 30 days after the last study drug dose. Patients who have not experienced PD will continue to be followed for disease response as per Table 3 or Table 4 until development

of PD, as determined by the Investigator. Patients with documented PD, as determined by the Investigator, will be followed on an every 3-month basis for survival until closure of the study by the Sponsor; follow-up for survival may be conducted via telephone.

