#### **11.9.** Efficacy Analyses

For the Dose Optimization Phase, all primary and secondary efficacy analyses will be performed using the Dose Optimization Efficacy Population and will be based on the Investigator's determination of response, with the IRC's determination of response used for supportive efficacy analyses. Analysis of the Expansion Phase primary and secondary efficacy analyses will be performed using the mITT population and will be based on the IRC's determination of response, with the Investigator's determination of response used for supportive efficacy analyses. All time to event analyses will present median times to event and 2-sided 95% confidence bounds. Censoring rules will be detailed in the SAP. Neither IRC or Investigator's determination will require confirmation by a second assessment.

Primary Efficacy Analysis:

• ORR will be tabulated using response determination by the Investigator (Dose Optimization) or IRC (Expansion). Best overall response and response assessments over time will be presented along with 2-sided confidence intervals

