3.5 Interim Analysis and Data Review

As noted in Section 3.3, during the dose optimization phase, the ORR for each dose optimization cohort will be reviewed when 5 patients are determined to be evaluable. If no response of CR or PR has been observed in the cohort then enrolment in that cohort will be discontinued. Evaluation of response in this analysis will be based on Investigator assessments.

In addition, at the conclusion of the Dose Optimization Phase, all available data will be reviewed and an optimal dose for the Expansion Phase will be selected. In addition to recommending an optimal dose, the Expansion Phase may also involve modifications of the study patient population, other aspects of entry criteria, and the inclusion of patients from geographic regions outside the US; any such changes will be documented in an amendment to the protocol. The Sponsor study team, in collaboration with the Investigators, will make the determination of duvelisib dose for the Expansion Phase of the study based on the totality of available safety and activity data. This evaluation does not constitute an interim analysis.

During the expansion phase, two assessments of ORR will be conducted. The first will be a preliminary assessment of ORR after approximately 15 subjects have had an initial assessment of response by the investigator. During this assessment, the data from the expansion phase will be reviewed in the context of data from the dose optimization phase.

The second assessment will occur after 40 patients have been followed for a minimum of 4 months from the last patient's first dose and assessed for response by the IRC. At that time, enrollment in the Expansion Phase may be held if ORR is less than 20%. The efficacy data (including durability of response) will be reviewed in combination with safety and PK and upon review, the study may be fully stopped for futility.

- Additional interim analyses will be used for planning purposes, FDA submission and discussion and possible publication of early efficacy and safety results. The final analysis of the study will be completed and submitted to health authorities and published as appropriate. The approximate timing of these interim analyses are when: At least 75 of expansion phase patients have been followed for a minimum of 6 months from the last patient's first dose and assessed for response by the IRC.

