- All patients enrolled prior to protocol v7.0 (101 patients) who have been followed for a minimum of 6 months from the last patient's first -scheduled response assessment (*i.e.*, 8 months from their first dose) and who have response assessed by the IRC.

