4.1 General Methods

Summary statistics will be presented by treatment group, unless stated otherwise.

Unless otherwise specified, descriptive statistics for continuous data will include the number of subjects with data to be summarized (n), mean, standard deviation, 25% quartile, median, 75% quartile, and minimum and maximum. The same number of decimal places as in the raw data will be presented when reporting the minimum and maximum, one more decimal place than the raw data will be presented when reporting mean and median, and 2 more decimal places than the raw data will be presented when reporting standard deviation.

Descriptive statistics for categorical/qualitative data will include frequency counts and percentages. The total number of subjects in the treatment group will be used as the denominator for percent calculations, unless stated otherwise. All percentages will be presented with one decimal, unless otherwise specified. Percentages equal to 100 will be presented as 100, and percentages will not be presented for zero frequencies.

Descriptive statistics associated with time-to-event analyses will include the number of events, the number of subjects censored, 25% quartile, median, 75% quartile, and 95% confidence interval for median. These statistics will be presented for all time-to-event analyses, unless stated otherwise.

Listings will be provided for selected endpoints.

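### Time to treatment discontinuation is summarised only in patients who have already stopped, so this disposition summary runs short, and moves from cut to cut, whenever patients remain on drug

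*SAP*

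**What the plan says.** SAP 5.1.1 (Disposition of Subjects) defines the summary in one sentence: "Time to treatment discontinuation will be summarized for subjects who have discontinued treatment at time of data cut-off". It describes no censoring, and no other section gives a Kaplan-Meier or other all-patient estimate of time to discontinuation.

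The surrounding provisions are:

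- **Treatment length.** Protocol 4.3 states that "no maximum duration of therapy has been set", so patients can be on drug at any cut.
- **Data cuts.** SAP 3.5 plans a futility look ("The second assessment will occur after 40 patients have been followed for a minimum of 4 months from the last patient's first dose") and an interim when "At least 75 of expansion phase patients have been followed for a minimum of 6 months from the last patient's first dose". A further interim covers the 101 patients enrolled before protocol v7.0, with at least 8 months from first dose. The two later interims are meant for planning, FDA submission and possible publication. SAP 3.3 triggers the final analysis by enrolment and evaluation for the primary endpoint, not by all patients having stopped.
- **Time-to-event format.** SAP 4.1: "Descriptive statistics associated with time-to-event analyses will include the number of events, the number of subjects censored", together with quartiles and a 95% CI for the median, unless stated otherwise. For efficacy, Protocol 11.9 adds: "All time to event analyses will present median times to event and 2-sided 95% confidence bounds".
- **Exposure.** SAP 5.1.7 summarises treatment duration, duration categories, cycles started and the proportion discontinued in the whole Safety Analysis Set.

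**The concern.** Selecting patients because their event happened before the cut is right truncation. Those left out are the ones still on treatment, whose times already exceed their follow-up and so tend to be the longest. What remains describes early stoppers, and how early depends on how long patients have been followed.

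Two things are at stake. A table titled as time to discontinuation is easily read as describing the treated population. And figures from successive cuts would differ because follow-up differs, even if the underlying distribution did not change.

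**Working it through.** The plan states no figure for time to discontinuation, so there is none to reproduce. The check covers direction, size, and what the exposure table supplies.

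**Direction.** Let d patients have stopped by the cut. The discontinued-only summary gives each of their times weight 1/d. Kaplan-Meier in all treated patients gives the same ordered times weights that never decrease with time and sum to at most 1. The first k Kaplan-Meier weights therefore sum to at most k/d, so the discontinued-only median cannot exceed the Kaplan-Meier median. In 3,000 simulated cuts of 101 patients it was longer in none. A tie needs the unusual case where ongoing patients have shorter times than all or nearly all of those who stopped.

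**Size.** These inputs are assumptions, because the documents give neither: time on treatment T is exponential with median m, and follow-up C is uniform from a to b months and independent of T.

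Share ongoing at the cut: π = m / [ln 2 × (b − a)] × (2^(−a/m) − 2^(−b/m)).

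For t no longer than a, the discontinued-only distribution is (1 − 2^(−t/m)) / (1 − π). Setting it to 0.5 gives:

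reported median = m × [1 − log2(1 + π)].

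The relative bias is then −log2(1 + π), which depends only on the share ongoing.

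Worked case, m = 6, a = 6, b = 12: π = 6/(0.693 × 6) × (0.5 − 0.25) = 0.361. The reported median is 6 × (1 − log2 1.361) = 6 × (1 − 0.444) = 3.33 months.

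| Follow-up (months) | True median | Ongoing | Reported median | Bias |
|---|---|---|---|---|
| 6-12 | 2.5 | 9% | 2.18 | −13% |
| 6-12 | 4 | 22% | 2.85 | −29% |
| 6-12 | 6 | 36% | 3.33 | −44% |
| 6-24 | 2.5 | 4% | 2.37 | −5% |
| 6-24 | 4 | 11% | 3.41 | −15% |
| 6-24 | 6 | 21% | 4.35 | −28% |
| 12-50 | 2.5 | 0.3% | 2.49 | −0.5% |
| 12-50 | 4 | 1.9% | 3.89 | −3% |
| 12-50 | 6 | 5.6% | 5.53 | −8% |

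The same 6-month true median is thus reported as 3.33, 4.35 or 5.53 months depending only on follow-up.

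**Shape.** A falling hazard enlarges the bias. With follow-up of 8-20 months and a true median of 4 months, the exponential gives 3.42 (−14%, 10.5% ongoing), while a Weibull with shape 0.7 gives 2.59 (−35%, 19.9% ongoing).

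**Exposure table (SAP 5.1.7).** It summarises min(T, C) in everyone.

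- *Median.* Nobody is cut off before a months, so a true median of a or less is recovered. In every row above, the all-patient median is 2.5, 4.0 or 6.0, the true value.
- *Mean.* For exponential times the expected value is (1 − π) × m / ln 2. With m = 6 and follow-up 6-12 months this is 0.639 × 8.66 = 5.53 against a true mean of 8.66.
- *Upper quartile.* In the same case it solves [(12 − t)/6] × 2^(−t/6) = 0.25, giving t = 8.15 against a true value of 12.
- *Side by side.* With follow-up of 6-24 months and m = 6, one report could show a median exposure of 6.0 months beside a median time to discontinuation of 4.35.

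**The case against.** The case for leaving the text alone has real force.

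- **The population is stated.** The sentence says whom it covers, and the result is a valid description of patients who stopped. It sits under disposition, is not among the study endpoints and feeds no decision rule. SAP 4.1 allows exceptions to its format. All of this stands.
- **Exposure is already reported in everyone.** A reader might infer that the report as a whole would understate time on drug. The documents do not support that: as shown above, the SAP 5.1.7 median is correct whenever it is no longer than minimum follow-up. What it does not supply is a censored estimate, or a sound mean and upper quartile.
- **Benefit is measured elsewhere.** A reader might also infer that durability would be understated in patients who respond. DOR, PFS and OS all use Kaplan-Meier with censoring (SAP 5.2.2), follow-up from first response is summarised in SAP 5.1.1, and SAP 5.2.1.1 plans swimmer's plots with end-of-treatment reasons.
- **Follow-up may be long.** The expansion dose was documented on 14 March 2019 and protocol v7.0 is dated 20 July 2021, so the 101 patients could have accrued over as much as about 28 months. First and last enrolment dates are not given, so this is only a bound. With follow-up of 8-36 months, true medians of 2.5, 4 and 6 are reported as 2.45, 3.7 and 5.0. The SAP is a final version of August 2023, so the interim cuts may already be past. This limits the size and not the direction. The final analysis does not wait for every patient to stop, so the change may still matter there.

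**Conclusion.** The point holds as a minor defect in a descriptive table. The SAP 5.1.1 summary is biased short, and is not comparable between cuts, whenever patients remain on drug. The bias vanishes once all have stopped.

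Its size cannot be taken from the documents. Under exponential times with medians of 2.5 to 6 months it runs from about 0-8% (roughly 6% or fewer ongoing, follow-up 12-50 months) to 13-44% (9-36% ongoing, follow-up 6-12 months), and it is larger under a falling hazard. These ranges rest on the assumed distribution, uniform follow-up, and independence of T and C. The share ongoing at the actual cut is the figure that matters.

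ORR, alpha, power and the time-to-event endpoints are untouched. The practical risk is a misread disposition table that may conflict, without explanation, with the exposure table in the same report.

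**What to change.** In SAP 5.1.1, estimate time to treatment discontinuation by Kaplan-Meier in the Safety Analysis Set, by phase and treatment, censoring patients still on drug at the data cut-off. Report the number discontinued, the number ongoing, the quartiles, and the median with 95% CI, as SAP 4.1 already sets out. The discontinued-only summary may stay as a supplement labelled as conditional on having stopped.

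A footnote to the SAP 5.1.7 duration table, giving the number ongoing and noting that their durations are incomplete, would explain any difference between the two medians.

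The cost is a sentence or two in the SAP and one table. No new data are needed: SAP 5.1.7 already uses first and last dose dates, and SAP 5.1.1 already identifies who has discontinued.
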